## PURPOSE & HYPOTHESIS

Our central hypotheses are that handheld spirometry is feasible for inpatient and at-home use and is equally efficacious at determining lung function when compared with bedside spirometry measurements. To test these hypotheses, we propose the following specific aims:

**Specific Aim 1:** Determine the correlation of SpiroPD handheld spirometry measurements with bedside Koko spirometry lung function.

**Hypothesis:** Correlation between the two lung function tests will be substantial for both hospitalized and ambulatory patients.

**Specific Aim 2:** To determine the feasibility, adherence, and preliminary management efficacy of home SpiroPD testing.

**Hypotheses:** (1) Patients will demonstrate substantial adherence to daily home spirometry testing; (2) medication adherence will increase significantly in patients who are adherent to daily home spirometry testing; (3) acute care utilization will decrease significantly in adherent patients.

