## METHODS OVERVIEW

We will enroll patients diagnosed with COPD both in the hospital and clinic setting and follow for 30 days. Participants will complete comparative lung function measurements with both devices while in the hospital or clinic at time of enrollment and at the 30-day follow up visit. Correlation will be assessed using Spearman's correlation coefficient. A high correlation ( $> 0.8$ ) will demonstrate the usefulness of the SpiroPD device in these patients in both settings. We will use the FDA-cleared (K 103575) SpiroPD device for its intended use.

At the time of their initial study visit, study participants will be given a SpiroPD device for use at home following instruction in the hospital or clinic. Patient adherence to daily testing over one-month will be monitored using real-time capture Wi-Fi-data from the SpiroPD data portal. Participant surveys will ascertain barriers and facilitators of daily spirometry lung function testing, and subject attitudes and beliefs about the usefulness of this testing for self-management. Adherence to medication use and utilization outcomes will be measured using patient logs. Acute care utilization will be measured via tracking of ED visits, hospitalizations, and urgent care calls. Information will be collected at the 30 day (+/- 1 week) visit through in-person (preferred) or phone call visits (if do not show for in person visit).

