## **DURATION**

Participants will be asked to use the SpiroPD device for 30 days after discharge from the hospital or starting the day after the clinic visit if recruited from clinic. They will be in the study for 30 days (with a window of +/- 1 week for the 30 day visit) from the time of enrollment.

Electronic data will be collected from the time of electronic medical record initiation at University of Chicago (11/1/2008) until 90 days past the day of enrollment.

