## **TYPE AND NUMBER OF EXPERIMENTAL SUBJECTS**

We will enroll 150 study participants.

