## STATISTICAL ANALYSES

**SA1:** Correlation between KoKo and SpiroPD measurements will be assessed using Spearman's correlation coefficient. A high correlation ( $> 0.8$ ) will demonstrate the usefulness of the SpiroPD device in these patients.

**SA2:** Feasibility process measures such as proportion of participants who adhere to the at-home use of SpiroPD lung function testing, adherence measures to treatment regimens, and estimates of efficacy as denoted by exacerbations and acute care utilization will be analyzed using descriptive statistics. Patient characteristic associated with increased SpiroPD use, treatment adherence, and efficacy of lung function testing will use McNemars, Fishers exact or Chi square testing for categorical variables and rank sum or t-tests for continuous variables.

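### SA2 tests patient characteristics without accounting for hospital versus clinic recruitment, so a characteristic that only marks setting can be reported as associated with use, adherence or utilization

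*Combined protocol and SAP*

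**What the plan says.** The Methods Overview puts two sources of participants into one study: "We will enroll patients diagnosed with COPD both in the hospital and clinic setting and follow for 30 days". The section on number of subjects gives one total, "We will enroll 150 study participants", with no split by source.

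The SA2 paragraph of Statistical Analyses summarizes outcomes descriptively ("estimates of efficacy as denoted by exacerbations and acute care utilization will be analyzed using descriptive statistics") and then plans association tests. For categorical variables: "Patient characteristic associated with increased SpiroPD use, treatment adherence, and efficacy of lung function testing will use McNemars, Fishers exact or Chi square testing". For continuous ones: "rank sum or t-tests for continuous variables". No stratum, covariate or regression model is named. McNemar's test is paired and does not bring setting in either.

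The two settings are named together in the Aim 1 hypothesis, "Correlation between the two lung function tests will be substantial for both hospitalized and ambulatory patients". That concerns agreement between devices, not SA2.

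**The concern.** Confounding by setting needs two things: the characteristic must differ between hospital and clinic recruits, and so must the outcome. The protocol makes both credible.

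- **Use window.** The Duration section starts device use at a different point in each setting: "Participants will be asked to use the SpiroPD device for 30 days after discharge from the hospital or starting the day after the clinic visit". Study participation, by contrast, runs for 30 days "from the time of enrollment". An inpatient spends part of the 30 days after enrollment still admitted; a clinic recruit does not.
- **Outcome risk.** The Background motivates the study by readmission within 30 days of a COPD hospitalization. It thus treats recently discharged patients as a high-risk group for acute care use, which is an SA2 outcome.
- **Case mix.** The inclusion criteria accept inpatients admitted for something other than COPD, such as heart failure. Prior-year hospitalizations, comorbidities and insurance type are collected, and could plausibly track setting.

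If both conditions hold, a pooled test can flag a characteristic that has no relation to the outcome among inpatients or among clinic patients. A reader of the pilot could then attribute low use or high utilization to the wrong feature of the patients.

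**Working it through.** **Plan's own figures.** The document states no rate, effect size or power for SA2. Its sample-size table serves the SA1 correlation only. That table does reproduce: for r = 0.23, ((1.960 + 0.842)/atanh(0.23))² + 3 = 146.1, against 145.92 printed. It does not bear on SA2.

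**Inputs.** The total of 150 is from the document. The 75/75 split, the prevalence of a binary characteristic in each setting (c_in, c_out) and the outcome rate in each setting (y_in, y_out) are assumptions. Within each setting the characteristic has no effect.

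**Pooled difference.** With equal groups and p = (c_in + c_out)/2, the difference in outcome rate between those with and without the characteristic is

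(c_in − c_out)(y_in − y_out) / [4p(1 − p)].

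It depends on the product of the two gaps and is zero if either gap is zero.

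- Large gaps, prevalence 70%/25% and adherence 40%/70%: (0.45 × −0.30)/(4 × 0.475 × 0.525) = −0.135. Directly, 34.125/71.25 = 0.479 with the characteristic and 48.375/78.75 = 0.614 without; the odds ratio is 0.58.
- Small gaps, prevalence 50%/40% and adherence 60%/70%: (0.10 × −0.10)/(4 × 0.45 × 0.55) = −0.010.

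**Rejection rates.** For each scenario, 20,000 trials were simulated and two statistics compared with 3.841: the pooled chi-square, and the Cochran-Mantel-Haenszel (CMH) statistic stratified by setting, [Σ(a_s − E_s)]²/ΣV_s. Here a_s is the number in setting s with both the characteristic and the outcome, and E_s and V_s are its hypergeometric mean and variance. Simulation standard error is about 0.15 points at 5% and 0.34 points at 39%.

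| Prevalence, hospital/clinic | Outcome rate, hospital/clinic | Pooled chi-square rejects |
|---|---|---|
| 50/50 | 45/65 | 4.9% |
| 70/30 | 50/50 | 4.9% |
| 50/40 | 60/70 | 5.5% |
| 60/40 | 60/70 | 6.0% |
| 50/25 | 60/70 | 6.7% |
| 60/40 | 45/65 | 8.0% |
| 50/25 | 50/70 | 10.1% |
| 60/25 | 50/70 | 14.2% |
| 70/25 | 50/70 | 20.6% |
| 50/25 | 40/70 | 16.5% |
| 60/25 | 40/70 | 26.0% |
| 70/25 | 40/70 | 38.9% |

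The CMH test rejected in 4.7% to 5.3% of trials throughout.

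**Sensitivity.** An acute-care-type outcome of 30%/10% with prevalence 70/30 gives 24%. With prevalence 70/30 and outcome 40/70, a 75/75 split gives 32%, and splits of 100/50 or 50/100 give 27% to 28%. A characteristic that almost identifies the setting (prevalence 90/10, outcome 40/70) gives 85%. That is an extreme case and is not carried into the conclusion.

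**The case against.** The strongest reply is that this is an exploratory screen in a pilot, and that the pooled association is a real quantity. In the scenarios above the pooled odds ratio truly differs from 1, so the chi-square test correctly rejects its own null. For the question of who uses the device, that marginal description is legitimate. Setting may also be a consequence of some characteristics, in which case stratifying answers a different question. This stands, and is why the unadjusted result should be kept. It does not make the unadjusted test sufficient, because the plan gives the reader no way to separate a characteristic from the place of recruitment.

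Other limits also stand. Pooling and one-at-a-time testing are inferred from the tests listed and the absence of any stratum; they are not stated. The inpatient and outpatient enrollment sections describe the device training in the same terms, so differing training content cannot be claimed. Several medical-record items, such as length of stay and admission labs, exist only for inpatients and cannot be stratified by setting.

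A reader might also infer that these associations are meant as predictors to guide later studies. The document does not say so. Statistical Analyses speaks of association, and the Background's remark about next-step studies concerns the usefulness of hand-held spirometry.

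**Conclusion.** The point holds as a gap that is cheap to close. SA2 names only unadjusted tests, setting is never accounted for, and the protocol gives setting a credible link to use, utilization and case mix. A characteristic that only marks setting can therefore be reported as associated with an SA2 outcome.

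The size rests wholly on assumed inputs. Measured against the null of no association within setting, pooled rejection is about 5% when the characteristic or the outcome barely differs by setting, 5.5% to 8% for the modest gaps tried, and 10% to 39% for prevalence gaps of 25 to 45 points with adherence gaps of 20 to 30 points.

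A reader might conclude that spurious findings will occur, or that the error rate is necessarily well above 5%. The document supports neither: it gives no setting split and no distribution of characteristics or outcomes by setting. The point concerns the SA2 association tests only and does not touch the KoKo–SpiroPD correlation.

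**What to change.** Amend the SA2 paragraph of Statistical Analyses as follows.

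1. For characteristics measured in both settings, make the association test one stratified by enrollment setting: Cochran-Mantel-Haenszel for categorical characteristics, and van Elteren or a regression with a setting term for continuous ones.
2. Show the unadjusted result beside it, labelled descriptive.
3. Report SpiroPD use, medication adherence and acute care utilization by setting as well as in total.
4. Analyse inpatient-only characteristics within inpatients.

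Setting is known for every participant, so no new data, visits or participants are needed. The cost is a change of wording, slightly more analysis, and some loss of power for characteristics strongly tied to setting.

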## **Medical Record and Administrative Data Collection**

The following data will be collected by the CRDW and merged with survey and device data:

- Admission labs (e.g., bicarbonate, hemoglobin, creatinine) (hospitalized patients)
- Admission and discharge medications, inpatient medications (hospitalized patients)
- Admission length of stay (hospitalized patients)
- Admit and discharge service (hospitalized patients)
- Procedures during hospital stay (ICD-10 coded procedure) (hospitalized patients)
- Index admission type (urgent or emergent vs elective) (hospitalized patients)
- Comorbidities, ICD-9 & ICD-10
- Number of ED visits in the 12 months prior to enrollment and during the study period
- Number of hospitalizations in the 12 months prior to enrollment and during the study period
- Number and type of outpatient visits in the 12 months prior to enrollment and during the study period

- Number of observation stays in the 12 months prior to enrollment and during the study period
- PFTs
- Prescriptions for medications
- EPIC Healthy Planet data, including follow up phone calls, medication education, etc
- Consults received
- Insurance types
- Cost accounting system data (eSimon) including expected pay, net expected pay, etc.

These data will be collected from the time of electronic medical record initiation at University of Chicago (11/1/2008) until 90 days past enrollment.

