## **DATA SAFETY MONITORING PLAN**

The PI will review monthly data reports reviewing recruitment, consent, intervention activities, adverse events, and follow-up. Although few, if any, intervention-related adverse events are anticipated in this observational study, the study population is at risk for poor outcomes, including life-threatening exacerbations and death. The PI will comply with prompt reporting of any unanticipated events to the IRB.

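### SA2 relates patient characteristics to the efficacy of home testing in a cohort with no comparator, so the associations are prognostic and cannot show in whom testing works

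*Combined protocol and SAP*

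**What the plan says.** Aim 2 (Purpose & Hypothesis) is "To determine the feasibility, adherence, and preliminary management efficacy of home SpiroPD testing". Its third hypothesis is that "acute care utilization will decrease significantly in adherent patients".

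Methods Overview describes one cohort: "study participants will be given a SpiroPD device for use at home following instruction in the hospital or clinic". The planned size is 150. No randomised, concurrent or historical group without the device is described, and the Data Safety Monitoring Plan calls the study observational.

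The SA2 paragraph of Statistical Analyses has two parts that matter here. The descriptive part says that "estimates of efficacy as denoted by exacerbations and acute care utilization will be analyzed using descriptive statistics". The next sentence is inferential: "Patient characteristic associated with increased SpiroPD use, treatment adherence, and efficacy of lung function testing will use McNemars, Fishers exact or Chi square testing", with rank-sum or t-tests for continuous variables. SA2 names no comparator, no adjustment and no characteristic-by-device interaction. It does not define efficacy again for this second sentence.

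Medical Record and Administrative Data Collection lists counts for the year before enrollment as well as for follow-up, for example "Number of hospitalizations in the 12 months prior to enrollment and during the study period". Data Sharing lists utilization before and after the study.

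**The concern.** To say that testing is more efficacious in one kind of patient is to say that the difference between outcome with testing and outcome without it varies by patient type. When everyone has the device, only the outcome with testing is observed. Comparing it across levels of a characteristic shows who has more events, which is prognosis.

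The two questions have different answers whenever a characteristic carries risk of its own. A risk marker can then be listed as a predictor of efficacy although the device does nothing. A characteristic that truly marks benefit can be missed, because the benefit brings a high-risk group down towards the others. At stake is what the report may say. Following the sentence as written would present risk factors as evidence about where home testing works.

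The point covers only the efficacy item in that sentence. Which characteristics go with SpiroPD use or with treatment adherence is a legitimate descriptive question in a single cohort.

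**Working it through.** **1. The plan's own figures.** SA2 has no stated power, sample size or event rate. The only sample-size table, after the exclusion criteria, is for the SA1 correlation. Its r = 0.23 row reproduces: ((1.960 + 0.842)/atanh(0.23))² + 3 = 146.1, against the printed 145.92. It has no bearing on this point.

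**2. What the tests estimate.** Let r₁(x) be the event risk with the device for patients with characteristic x, and r₀(x) the risk without it.

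- Efficacy at x is r₀(x) − r₁(x). Difference in efficacy across x: [r₀(1) − r₁(1)] − [r₀(0) − r₁(0)].
- The SA2 tests on follow-up events compare r₁(1) with r₁(0).
- With no device effect, r₁ = r₀. The difference in efficacy is then zero, but r₁(1) − r₁(0) equals the full difference in underlying risk.

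No sample size closes that gap, since r₀ is never observed.

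**3. Illustration, no device effect.** From the documents: n = 150. Assumed: a binary characteristic splitting patients 75/75 or 45/105 (high risk/low risk), the event risks below, two-sided 0.05.

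Formula: probability = Φ[(|p₂ − p₁| − 1.96·se₀)/se₁], with se₀ = √[p̄(1 − p̄)(1/n₁ + 1/n₂)] and se₁ = √[p₁(1 − p₁)/n₁ + p₂(1 − p₂)/n₂].

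- 10% v 20%, 75/75: se₀ = 0.0583, se₁ = 0.0577; (0.10 − 0.1143)/0.0577 = −0.247; probability 0.40.
- 10% v 30%, 75/75: se₀ = 0.0653, se₁ = 0.0632; (0.20 − 0.1280)/0.0632 = 1.138; probability 0.87.

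The same by exact enumeration of the uncorrected chi-square test:

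| Risk, low v high | Formula, 75/75 | Exact, 75/75 | Exact, 45/105 |
|---|---|---|---|
| 10% v 15% | 0.15 | 0.15 | 0.17 |
| 10% v 20% | 0.40 | 0.41 | 0.40 |
| 10% v 25% | 0.68 | 0.70 | 0.66 |
| 10% v 30% | 0.87 | 0.89 | 0.85 |
| 15% v 30% | 0.60 | 0.60 | 0.56 |
| 15% v 15% | – | 0.05 | 0.05 |

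Fisher's exact test, simulated at 75/75, gives 0.34 for 10% v 20% and 0.83 for 10% v 30%.

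**4. Illustration, real difference in benefit.** Suppose the device halves risk in high-risk patients (30% to 15%) and does nothing in low-risk patients. If the low-risk group stays at 15%, the observed comparison is 15% v 15%, and the true modifier is flagged about 5% of the time. If the low-risk group stays at 10%, the comparison is 10% v 15%: it is flagged 15–17% of the time, and almost always with the benefiting group looking worse.

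**5. Before/after reading.** Suppose efficacy means annualised follow-up use minus use in the prior 12 months. Simulation with no device effect, 75/75, assumed annual rates of 0.5 v 1.5, 1 v 2 and 1 v 3, and gamma-Poisson variation between patients:

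| Test | 90-day window | 30-day window |
|---|---|---|
| Chi-square on improved or not | 15–41% | 25–70% |
| Rank-sum on the change | 5–7% | 23–53% |

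This simulation includes no recovery after an index admission and no selection for a recent bad period. Either could produce change that differs by characteristic.

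**6. What would answer the question.** With an assumed control arm, a characteristic-by-device interaction test flags the same pure risk marker (10% v 30%, no device effect) at about the nominal rate: 0.056 at n = 150 and 0.042 at n = 600.

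**The case against.** **The term is undefined, and the plan may intend a before/after measure.** SA2 does not say what efficacy means in the characteristics sentence. McNemar is a paired test, Aim 2 speaks of a decrease, prior-year counts are extracted, and Data Sharing lists use before and after the study. This stands as a fair reading, and it weakens any claim that the tests simply sort patients by risk: rank-sum on change over 90 days is close to nominal. It does not rescue the analysis. Without a comparator, change combines any device effect with regression to the mean and recovery after admission, and both can vary by characteristic.

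**Adherent versus non-adherent patients supply a contrast.** Adherence is self-selected, and the characteristics sentence does not use that contrast.

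**It is a pilot.** The aim is called preliminary and the efficacy estimates themselves are descriptive. That lowers the consequence but does not change what the tests estimate.

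A reader might infer three stronger points that the documents do not support:

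- *That the plan states a null of equal benefit across patient types.* SA2 states no null. The problem is an undefined efficacy label on an association test.
- *That 40–89% is an inflated type I error rate.* It is ordinary power to detect a risk difference that was put in by assumption. A characteristic unrelated to risk is flagged about 5% of the time.
- *That the resulting list would steer the target population of later trials.* Background ties next-step studies to showing that handheld spirometry is useful as an objective measurement. No section says that SA2 characteristics will select patients.

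**Conclusion.** The point holds as a mismatch between label and analysis. Associations between patient characteristics and exacerbations or acute-care use, in a cohort where all are given the device, are prognostic. They cannot show in whom testing is efficacious, on either reading of the undefined term. That conclusion follows from the design and needs no assumed figure.

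The size is illustrative only. The 40–89% range assumes risks from 10% v 20% to 10% v 30%, the two splits shown, and chi-square on follow-up events. A weaker marker (10% v 15%) gives 15–17%. The documents do not say which characteristics carry risk in this population, so the number of listed predictors that would be pure risk markers cannot be estimated.

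**What to change.** In the SA2 characteristics sentence, replace the efficacy item with *exacerbations and acute-care use during follow-up*. Add: *These are prognostic associations among device recipients and will not be reported as identifying who benefits from SpiroPD.* Leave the tests for SpiroPD use and treatment adherence as they are.

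Reporting each association with adjustment for use in the prior 12 months, from counts already extracted, is optional. It would show which associations only reflect earlier use, but it would not identify benefit.

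The cost is two lines of SAP text and no new data. The one thing given up is a claim about who benefits, which the single-cohort design cannot support.

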## POTENTIAL RISKS AND BENEFITS

The subject may be uncomfortable answering some interview questions. All subjects will be told that they can refuse to answer any question.

Loss of confidentiality. To help ensure that patients' health information remains private, we will restrict access to data collected for our study to study personnel only (via use of password-protection and locked cabinets for study documents). Study ID numbers will be generated and will be used when discussing and/or reviewing data at study meetings. Also, study reports will report results in aggregate and not contain information that can be used to identify individual patients.

Spirometry is safe and is commonly used to measure disease severity but can cause some minor chest soreness or lightheadedness.

You may not understand the data you see on your Spiro PD device. Use your best clinical judgement and care for your COPD as you normally would. Our research team is always available if you're not feeling well and would like to speak with a member of our COPD team.

